6.4. Data management and statistical analyses

6.4.1. Data management

The pen-and-paper questionnaires will be returned by the participants to the researchers at the seminar. Data entry from pen-and-paper questionnaires into a SPSS dataset will take place at the CVderm. 10% of cases will be double-checked by an independent data analyst by comparing SPSS data to the original questionnaires, to detect systematic errors of data entry. Data entered online will be exported from Unipark. The full SPSS dataset will be analyzed for plausibility by application of appropriate algorithms. Implausible data will be corrected or defined as missing values.

6.4.2. Statistical analysis

The statistical analyses will be conducted with the Statistical Package for the Social Sciences (SPSS v.27.0; IBM Corp., Armonk, NY). Descriptive statistics, i.e., absolute/relative frequencies and percentages for categorical variables and minimum, maximum, median, mean and standard-deviations for continuous variables, will be obtained for the total sample and subgroups of participants (e.g., by profession). The reliability of all questionnaires will be examined before conducting inference analyses, by calculating the Cronbach’s Alpha coefficients, considering $\alpha \geq 0.70$ as acceptable and $\alpha \geq 0.80$ as optimal.¹⁴ Assumptions of normality and sphericity will be checked by means of Shapiro-Wilk and Mauchly's Test of Sphericity, respectively.

Intervention effects on the primary outcomes will be analysed by means of 2 (Group: intervention, control) x 3 (Time: t0, t1, t2) repeated-measures analyses of variance (ANOVA). Subgroup analyses will be performed to assess potential differences between the professions. Intervention effects on the primary outcomes by profession will be analysed through 2 (Group: intervention, control) x 3 (Time: t0, t1, t2) x 3 (Profession: beauty, nurses, physical therapists) repeated-measures ANOVAs. The significance level will be established at a p-value ≤ 0.05 . Bonferroni correction for multiple testing will be applied. Effect sizes will be reported as η_p^2 , with $\eta_p^2 < 0.06$ indicating a small effect, $\eta_p^2 \geq 0.06$ indicating a medium effect and $\eta_p^2 \geq 0.14$ indicating a large effect.¹⁵ Post-hoc pairwise comparison will be used to further examine significant effects.

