Study Protocol

Refinement of the *ECHT-intervention* against stigmatization of people with visible chronic skin diseases for further target groups

“Beruf und Gesundheit in körpernahen Dienstleastungen“ (BEGINN)

Principal investigator:

[name]. [name]

Co-investigators:

PD [name]
[name]

Sponsor:

Eucerin, Beiersdorf

Study coordination:

CVderm 
German Center for Health Services Research
in Dermatology

Institute for Health Services Research in Dermatology and Nursing (IVDP)
University Medical Center Hamburg-Eppendorf (UKE)
[name]
E-Mail: [contact]
[contact]

1. Synopsis

Short title	Destigmatization of skin diseases in the public
Sponsor	Beiersdorf / Eucerin Social Mission Programme
Collaborators	German Psoriasis Association (Deutscher Psoriasis Bund e.V., DPB)
Research objectives	The objective of this project is to adapt and test the “ECHT-intervention” for feasibility and effectiveness in professions dealing with health and body care (i.e. hairdressers, cosmetologists, nurses, and physiotherapists/occupational therapists).
Study design	A 3-hour-intervention including self-experience/exercises, education and a patient encounter will be developed in an interdisciplinary expert group with patient participation. The evaluation will follow a randomised controlled design against a control group receiving a non-stigma-related intervention. Eligible participants will be professionals from the following branches: hairdressers, cosmetologists, nurses, physiotherapists/occupational therapists. Feasibility and effectiveness with regard to primary (stigmatising attitudes) and secondary outcomes (satisfaction with the intervention) will be assessed at three time points: baseline/before the intervention, immediately after the intervention, 3-month follow-up.
Estimated number of participants	n = 120 (30 per profession)
Outcomes	The main outcome is stigmatising attitudes, which will be assessed by desire for social distance, agreement with skin disease-related misconceptions (e.g. psoriasis myths), agreement with skin disease-related stereotypes, (each adapted from Pearl et al. and reported and intended behaviour towards people with skin disease (Reported and Intended Behaviour Scale (RIBS); adapted from Evans-Lacko et al.). In addition, sociodemographic information, such as age and gender, will be recorded.
Data analysis	Effects will be analysed using mixed repeated-measures analysis of variance.

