6.2. Participants

6.2.1. Number of participants

According to an a priori sample size calculation using G*Power¹¹ (F-tests for repeated measures ANOVA, within-between interaction) with the effect size obtained by Weinberger et al.¹⁰ (interaction effect for behavioural intentions: $\eta_p^2 = 0.02$), 82 participants are needed to obtain a power of 0.80 ($\alpha = 0.05$). To account for multiple testing and a potential drop-out rate of up to 20% at follow-up, we aim to include 120 participants in total.

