6.3. Outcomes

Participants will be asked to report their sociodemographic information and fill in the following self-report questionnaires via the platform Unipark (<http://www.unipark.com>) or using pen and paper at three time points, immediately before (T0) and after (T1) participating in the seminar, and 3 months later (T2):

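### The primary repeated-measures ANOVA, run in its standard form, discards the T0 and T1 scores of everyone who misses T2: up to 24 of 120 participants, with possible bias of unknown direction

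*Protocol*

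**What the plan says.** Protocol 6.4.2 fixes the primary model: "Intervention effects on the primary outcomes will be analysed by means of 2 (Group: intervention, control) x 3 (Time: t0, t1, t2"), as repeated-measures ANOVAs run in "Statistical Package for the Social Sciences (SPSS v.27.0; IBM Corp., Armonk, NY"). The synopsis agrees: "Effects will be analysed using mixed repeated-measures analysis of variance". Two further statements show that the classical between-within ANOVA is meant, not a likelihood-based mixed model. Section 6.4.2 says "Assumptions of normality and sphericity will be checked by means of Shapiro-Wilk and Mauchly's Test of Sphericity, respectively", and section 6.2.1 sizes the trial with the G*Power F-test for a within-between interaction.

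Section 6.2.1 gives multiple testing and "a potential drop-out rate of up to 20% at follow-up" as the reasons for enrolling 120 participants rather than 82. Section 6.3 places the questionnaires "immediately before (T0) and after (T1) participating in the seminar, and 3 months later (T2"). Section 6.4.1 mentions missing values only for implausible entries. Section 6.1 allocates whole seminars, not individuals, to the two arms.

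**The concern.** A classical repeated-measures ANOVA needs a complete T0-T1-T2 record. A participant who completes both questionnaires on the seminar day but not the one at 3 months drops out of the whole analysis, including the T0-T1 comparison for which nothing is missing. The protocol itself expects this pattern, because its drop-out allowance is for follow-up.

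Two things are at stake. The first is precision: observed data are not used. The second is validity: whether someone answers at T2 may depend on how they responded at T1, and possibly not in the same way in both arms, since only one arm covers stigma and meets a patient. A larger sample compensates for lost numbers but does not remove selection of this kind.

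**Working it through.** **1. The plan's sample size.** Inputs from 6.2.1: partial eta squared 0.02, alpha 0.05, power 0.80. Assumed, because not stated (G*Power defaults): 2 groups, 3 measurements, correlation 0.5, sphericity.

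- f² = 0.02/0.98 = 0.0204
- lambda = f² × N × 3/(1 - 0.5)
- df = 2 and 2(N - 2)

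For N = 82, lambda = 10.04 and power = 0.809. For N = 80, power is 0.799. With equal groups the stated 82 is reproduced.

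**2. Data lost at the planned upper limit of drop-out.**

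- Excluded: 0.20 × 120 = 24, leaving 96.
- Scores used per outcome by the ANOVA: 96 × 3 = 288.
- Scores available: 120 + 120 + 96 = 336.
- Discarded although observed: 336 - 288 = 48.
- Widening of the T0-T1 interval: sqrt(120/96) = 1.118, about 12%. This treats participants as independent.

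**3. Power with the formula of step 1.** The second alpha is 0.05/4 = 0.0125, on the assumption that the Bonferroni correction spans the four primary outcomes of 6.3.1.

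| Complete cases | alpha 0.05 | alpha 0.0125 |
|---|---|---|
| 96 | 0.87 | 0.72 |
| 120 | 0.94 | 0.84 |

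A model using all observed scores lies between the two rows, because it cannot recover the missing T2 scores.

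**4. Possible bias in the T0-T1 effect.** The protocol gives no drop-out mechanism, SD or correlation, so every input here is assumed: true effect -0.30 SD, SD 1, correlation 0.5, 20% drop-out per arm, and log-odds of drop-out rising by 0.5 to 1.0 per SD of the T1 score.

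Let z be a participant's T1 deviation from the arm mean. The expected T0 deviation is then 0.5z, so the completers' mean change in an arm equals the true change plus (1 - 0.5) × E[z | stays]. Numerical integration, with the intercept set for 20% drop-out, gives E[z | stays] = -0.096 (slope 0.5) and -0.173 (slope 1.0). It is 0 when drop-out does not depend on T1.

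| Arm in which drop-out depends on T1 | Slope 0.5 | Slope 1.0 |
|---|---|---|
| Intervention only | -0.30 - 0.5 × 0.096 = -0.348 | -0.30 - 0.5 × 0.173 = -0.387 |
| Both, 20% in each | -0.300 | -0.300 |
| Control only | -0.30 + 0.5 × 0.096 = -0.252 | -0.30 + 0.5 × 0.173 = -0.213 |

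If both arms share one rule, intercept included, with 20% drop-out on average, the values are -0.295 and -0.283, slightly conservative. If everyone with T0 and T1 is analysed, the expected value is -0.30 in every row, because no T0 or T1 score is missing.

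**The case against.** The protocol nowhere says that incomplete records are deleted. That follows from how the named method works in its standard form. An SAP that is not shown could impute T2, or could run the post-hoc T0-T1 comparison on everyone seen at T1. This is a fair limit, and the point therefore concerns the ANOVA in its standard form. It is still more than a detail left to the SAP, because the protocol names a primary model that has no place for a partial record.

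The loss of numbers has been planned for. The protocol says up to 20%, so 24 is a ceiling, and 96 exceeds 82. A reader might infer that the trial misses its stated power. It does not at alpha 0.05, and the 0.72 depends on how the Bonferroni correction is applied.

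A reader might also infer that the result is valid only if drop-out is completely at random, or that analysing completers favours the intervention. Neither is supported. Drop-out rates that merely differ by arm, or drop-out that depends on T0 by the same rule in both arms, leave the group difference in change essentially unbiased. Where bias does arise, it can go either way.

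On sphericity, the protocol plans Mauchly's test, so the assumption has not been overlooked. It bears on the error rate of the F-test, not on this bias.

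**Conclusion.** The point holds as a recommendation to change the primary model. It does not show that the trial fails its stated design target. At the protocol's upper limit of drop-out, the standard ANOVA excludes 24 of 120 participants and 48 observed scores per outcome, and widens the T0-T1 interval by about 12%. Stated power at alpha 0.05 is kept (0.87). Under a four-outcome Bonferroni correction, which is an assumption, it is 0.72 against 0.84 with complete data.

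Bias in the T0-T1 effect is possible if drop-out depends on the T1 response differently by arm. In the illustration it reaches about 0.05 to 0.09 SD on a true effect of 0.30 SD, in either direction. These sizes rest wholly on assumed inputs. The documents give no basis for predicting the direction.

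**What to change.** In 6.4.2, replace the 2 x 3 ANOVA with a likelihood-based linear mixed model (SPSS MIXED, REML) with group, time and their interaction and an unstructured within-person covariance. Use all observed scores of all participants, in the arm to which their seminar was assigned. Include a seminar random effect: seminars are the randomised units, and a model with only a within-person covariance would still treat people from the same seminar as independent. Report the group contrasts at T1 and T2, and keep the completers-only ANOVA as a sensitivity analysis. Align the synopsis wording.

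The model is valid under missing-at-random and does not need sphericity, which the current plan only tests.

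The cost is small: no new data, visits or software, and somewhat more modelling work. Partial eta squared would be replaced by model-based differences with confidence intervals, or reported alongside them.

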6.1. Study design and procedures

Cross-sectional interventional study on health and body care professionals (i.e., hairdressers, cosmetologists, nurses, physiotherapists/occupational therapists) recruited in the area of Hamburg, Germany.

Participants will sign up for one of the seminar dates through the study website. Seminars will be randomly assigned to be intervention or control seminar.

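### The primary Group x Time ANOVA leaves out profession, although the sample is planned by profession; adding it is a nearly free gain in precision

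*Protocol*

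**What the plan says.** Section 6.4.2 states the primary model: "Intervention effects on the primary outcomes will be analysed by means of 2 (Group: intervention, control) x 3 (Time: t0, t1, t2"), as repeated-measures ANOVA. It is applied to the four primary scales of 6.3.1.

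Profession enters only afterwards: "Subgroup analyses will be performed to assess potential differences between the professions". The model for that purpose is the same ANOVA extended by "x 3 (Profession: beauty, nurses, physical therapists) repeated-measures ANOVAs".

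The synopsis gives the estimated sample as "n = 120 (30 per profession"), over four groups: hairdressers, cosmetologists, nurses, and physiotherapists/occupational therapists. Section 6.2.1 sets only the total of 120.

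On allocation, section 6.1 says "Participants will sign up for one of the seminar dates through the study website" and "Seminars will be randomly assigned to be intervention or control seminar". It does not say whether a seminar is open to all professions or to one, how many seminars there are, or whether allocation is stratified by profession.

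**The concern.** The Group x Time test compares changes within persons, so stable differences in level between professions cancel. Differences in change do not. If one profession moves more than another between T0 and the later visits in both arms, for instance because the other already scores low and has little room to improve, a model with Group and Time alone counts that spread as error. Profession is known for every participant, so this part of the error can be removed at almost no cost.

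A second, conditional effect concerns the realised estimate. Whole seminars are randomised. If each seminar held one profession and allocation ignored profession, the arms could differ in profession mix by chance, and a profession difference in change would then enter the unadjusted Group x Time estimate for that allocation.

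**Working it through.** **1. The plan's own figure.** Section 6.2.1 uses G*Power ("F-tests for repeated measures ANOVA, within-between interaction") with "interaction effect for behavioural intentions: $\eta_p^2 = 0.02", power 0.80, alpha 0.05, and reports 82 participants. Take k = 2 groups, m = 3 times, no sphericity correction, and correlation rho = 0.5 (the last two are assumptions).

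- f² = 0.02/0.98 = 0.0204
- lambda = f² · N · m/(1 − rho) = 0.0204 · 82 · 3/0.5 = 10.04
- df = (k−1)(m−1) = 2 and (N−k)(m−1) = 160
- Power = 80.9%. The smallest N is 81, or 82 with equal arms. The stated figure reproduces.

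**2. Cost of omitting profession.** With 20% drop-out, 120 · 0.8 = 96 remain at follow-up, and the error df are (96−2) · 2 = 188. Four profession groups with their time interaction use 3 · 2 = 6 of these; three levels use 2 · 2 = 4. Let R² be the share of within-person error variance that profession x time explains. The documents give no value, so a range is shown. Adjustment changes lambda to lambda/(1 − R²). The alpha of 0.0125 is 0.05/4, on the assumption that the planned Bonferroni correction covers the four primary scales.

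| Assumed R² | N = 96, alpha 0.05 | N = 96, alpha 0.0125 |
|---|---|---|
| Profession omitted | 87.1% | 72.2% |
| Added, R² = 0 | 87.1% | 72.2% |
| Added, R² = 2% | 87.8% | 73.3% |
| Added, R² = 5% | 88.8% | 75.0% |
| Added, R² = 10% | 90.5% | 77.8% |

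The gain at R² of 5% and 10% is 1.7 and 3.4 points at alpha 0.05, and 2.8 and 5.6 points at alpha 0.0125. For scale, if two professions change more than the other two by 0.4 SD of the change score, the between-profession variance is 0.2² = 0.04, and R² = 0.04/1.04 = 3.8%.

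**3. Chance imbalance, only under an assumed seminar format.** Assume 12 single-profession seminars of 10, three per profession, allocated 6:6 without stratification, and the 0.4 SD difference above in both arms. If j of the six high-change seminars fall in the intervention arm, the distortion is 0.4 · (2j − 6)/6.

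- There are C(12,6) = 924 allocations. Exact balance (j = 3) occurs in C(6,3)² = 400.
- A distortion of at least 0.133 SD occurs in 524/924 = 57%.
- A distortion of at least 0.267 SD occurs in (36 + 36 + 1 + 1)/924 = 74/924 = 8%.
- Its mean is zero and its SD is 0.121. With a 0.2 SD profession difference the SD is 0.060.

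**4. Type I error by simulation.** No true effect, 96 completers, change score, 3,000 replicates per setting, no seminar effect beyond profession. With mixed-profession seminars the unadjusted test stayed at 4 to 5%. With single-profession, unstratified seminars:

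| Seminars | R² = 5% | R² = 10% |
|---|---|---|
| 8 | 12.7% | 21.6% |
| 12 | 9.1% | 15.7% |
| 16 | 7.2% | 11.6% |

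Adding profession brought these to between 5.1% and 5.8%. The mean estimated effect was about zero in every setting. With 8 seminars, some 8 to 10% of simulated allocations could not be adjusted at all, because arm and profession coincided completely.

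**The case against.** The strongest reply is that profession is already modelled. The 2 x 3 x 3 ANOVA covers every primary outcome, and a full-factorial fit also yields a profession-adjusted Group x Time test. That is true, so profession is not absent from the plan. But the plan presents that model as a subgroup analysis, it adds the three-way interaction, and it uses three levels where the synopsis lists four groups. It does not adjust the test that section 6.4.2 names for the intervention effect.

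A second reply is that covariates can be left to the analysis plan. Here, though, the protocol states the primary model outright.

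Several stronger readings are tempting, and the documents do not support them:

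- **That the primary effect is biased, or partly a comparison of professions.** Randomisation makes the imbalance average to zero. It matters only for single-profession, unstratified seminars, and section 6.1 settles neither point.
- **That the imbalance exceeds a third of the planned effect.** This takes partial eta squared as d²/[12(1 − rho)], so d = 0.35 SD for a difference sustained at T1 and T2, and 0.133/0.35 = 38%. The specification that reproduces 82 implies d² = 18f² = 0.367, so d = 0.61 SD (at rho = 0.5 the change-score SD equals the raw SD), and the ratio is 22%.
- **That profession is a quota or stratum that the analysis must respect.** The figure of 30 per profession is part of an estimated sample size. No cap or stratum is stated.
- **That the plan expects professions to differ in change.** It speaks only of potential differences, in the context of intervention effects by profession.

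It is also fair to say that any type I inflation here is at root a clustering problem. A profession term removes only the part of seminar variance that profession explains.

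**Conclusion.** The point stands as a free improvement. Omitting profession does not invalidate the primary test. It leaves removable variance in the error term, worth about 1.7 to 3.4 power points at alpha 0.05 or 2.8 to 5.6 at 0.0125 with 96 completers, if R² is 5 to 10%, and nothing if R² is zero. R², rho = 0.5 and a Bonferroni family of four are assumptions.

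The distortion of the realised estimate and the type I inflation are possible but not shown. They depend on the number and make-up of seminars and on how these are allocated, none of which the protocol gives. Where those conditions hold, the profession term protects against the profession part of the problem only.

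**What to change.** In section 6.4.2, pre-specify profession and profession x time as terms in the primary repeated-measures model for all four primary outcomes, whatever allocation results. Keep Group x Time x Profession as the separate subgroup test.

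Use one coding of profession in both models. This means reconciling the four groups of the synopsis with the three levels of 6.4.2.

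The cost is one line of wording and syntax and at most 6 of 188 error degrees of freedom. Power is practically unchanged if professions do not differ. Seminar clustering needs its own provision.

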5.1. Objectives

This project aims to modify the “ECHT” intervention for health and body care professions and

evaluate its effectiveness. It was hypothesized that the intervention group would show a larger reduction in stigmatising attitudes towards people with visible chronic skin diseases compared to the control group.

6. Study protocol

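### The 2 x 3 ANOVA is a valid test, but by treating the pre-seminar score T0 as an outcome level it gives up precision that data already collected could supply

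*Protocol*

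**What the plan says.** Section 6.4.2 fixes the primary analysis as "2 (Group: intervention, control) x 3 (Time: t0, t1, t2) repeated-measures analyses of variance (ANOVA". It extends this to a 2 x 3 x 3 ANOVA for profession. Neither model has a baseline covariate. The planned effect size is partial eta squared, and pairwise comparisons follow only where an effect is significant.

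Section 6.3 places the measurements "immediately before (T0) and after (T1) participating in the seminar, and 3 months later (T2"). Section 6.1 states: "Seminars will be randomly assigned to be intervention or control seminar". The hypothesis in section 5.1 is that "the intervention group would show a larger reduction in stigmatising attitudes towards people with visible chronic skin diseases compared to the control group".

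Section 6.2.1 sizes the trial on "F-tests for repeated measures ANOVA, within-between interaction" with partial eta squared 0.02, alpha 0.05 and power 0.80. The result is 82 participants, raised to 120 for multiple testing and up to 20% drop-out.

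**The concern.** Random assignment makes the expected arm difference at T0 zero. The interaction test nevertheless leaves that difference free and in effect compares changes from T0, so the sampling error of T0 enters the treatment contrast in full. Conditioning on T0, or constraining its mean to be equal between arms, uses what randomisation already provides.

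What is at stake is precision. There are four primary outcomes and a Bonferroni correction. If that correction covers those four outcomes, the planned test falls below the protocol's own power target even with 96 completers (shown below). The 2-df F also combines T1 and T2, and the plan promises no adjusted difference with a confidence interval at either time unless an effect is significant.

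**Working it through.** **Inputs.** From the protocol: two groups, three times, partial eta squared 0.02, alpha 0.05, N = 82, target 120, drop-out up to 20%. The last two give 120 x 0.8 = 96 completers. Assumed: compound symmetry with correlation ρ, sphericity (epsilon 1), and alpha 0.05/4 = 0.0125, because the Bonferroni family is not named.

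**The plan's own figure.** f² = 0.02/0.98 = 0.0204. For the within-between interaction, λ = f² x N x 3/(1 − ρ), with df 2 and 2(N − 2). At ρ = 0.5, the G*Power default, N = 82 gives λ = 10.04 and power 0.809. The smallest N is 81, or 82 with equal groups. The figure reproduces, so ρ = 0.5 is the implied value although it is not stated. It also depends on G*Power's default effect-size option; the 'as in SPSS' option gives 240. That affects absolute power, not the relative gain below.

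**Gain from using T0 as baseline.** Let d be the effect at (T1, T2), S the covariance matrix of (T0, T1, T2) and C the contrasts T1 − T0 and T2 − T0. Non-centrality is proportional to d′(CSC′)⁻¹d for the interaction and to d′S₍₁₂|₀₎⁻¹d given T0. For a sustained effect the ratio of the two is 3/(1 + 2ρ). For an effect gone by T2 it is 3(1 + ρ)/(2(1 + 2ρ)).

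| Effect at T1, T2 | Interaction, ρ 0.5 | Given T0, ρ 0.5 | Ratio, ρ 0.5 | Ratio, ρ 0.3 | Ratio, ρ 0.8 |
|---|---|---|---|---|---|
| 1, 1 | 1.333 | 2.000 | 1.50 | 1.88 | 1.15 |
| 1, 0.5 | 1.000 | 1.375 | 1.375 | 1.66 | 1.12 |
| 1, 0 | 1.333 | 1.500 | 1.125 | 1.22 | 1.04 |

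**Power with 96 completers, alpha 0.0125, ρ = 0.5.** λ = 0.0204 x 96 x 6 = 11.755. With df 2 and 188 the ANOVA has power 0.72. Multiplying λ by 1.125, 1.375 and 1.50 gives 0.79, 0.88 and 0.91. With 92 error df for the adjusted test these become 0.77, 0.87 and 0.90.

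**Clustering.** All the figures above treat individuals as independent. As an illustration, take one post-seminar time, total variance 1, total correlation 0.5, m participants per seminar, and a seminar effect with ICC τ that persists fully over time. That effect cancels in change from T0. An individual-level covariate with within-seminar slope b = (0.5 − τ)/(1 − τ) removes only part of it. Relative to change, the variance is

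mτ(1 − b)² + (1 − τ)(1 − b²).

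For m = 12 and τ = 0.20, b = 0.375, which gives 2.4 x 0.391 + 0.8 x 0.859 = 1.62. If the seminar-mean T0 is also used, the relative variance is m(V − c²/V), with V = τ + (1 − τ)/m and c = τ + (0.5 − τ)/m.

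| ICC | Individual T0 only, m = 12 | Plus seminar mean, m = 12 | Individual T0 only, m = 20 | Plus seminar mean, m = 20 |
|---|---|---|---|---|
| 0.02 | 0.81 | 0.80 | 0.85 | 0.82 |
| 0.05 | 0.90 | 0.84 | 1.01 | 0.87 |
| 0.10 | 1.09 | 0.88 | 1.34 | 0.91 |
| 0.20 | 1.62 | 0.92 | 2.25 | 0.95 |

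Values above 1 are worse than change from T0. Using T0 at both levels stays below 1 throughout.

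**The case against.** The strongest reply is that nothing in the plan is wrong. The hypothesis speaks of a larger reduction, the interaction over T0, T1 and T2 tests exactly that, and section 6.2.1 sizes the trial on the same test. This stands. A reader might infer that the ANOVA is biased or invalid; the documents do not support that.

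A reader might also take the gain to be 50%, with power of 0.91. That is the most favourable pattern at ρ = 0.5: an equal effect at T1 and T2. The protocol states neither the correlation nor the course of the effect, and at ρ = 0.8 with an effect gone by T2 the gain is 4%.

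A third tempting reading is that adding T0 as an ordinary covariate has no downside. With randomised seminars this fails, as the second table shows: where seminar differences persist, the individual covariate alone can do worse than change.

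Finally, it would be too strong to say that the plan gives no information at each time point. Descriptive means and post-hoc pairwise comparisons are planned. What remains is that the comparisons depend on significance and that no confidence interval is specified.

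A statistical analysis plan that is not shown could add covariates, but the protocol already names its model, and that model has none.

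**Conclusion.** The point holds as a loss of efficiency and should be acted on, although the trial would not be invalid without the change. For independent individuals under compound symmetry, the direction does not depend on the unknown correlation: both closed-form ratios exceed 1 for every ρ below 1. The size does depend on it, from 4% to 88% in non-centrality over ρ 0.3 to 0.8. At the implied 0.5, power rises from 0.72 to between 0.79 and 0.91, given 96 completers, the assumed alpha of 0.0125 and the protocol's effect-size entry. These powers are too high for both models, because the number of seminars and the ICC are not given. For the same reason the gain under clustering cannot be fixed from the protocol. The illustration shows only that the gain survives if T0 is used at both individual and seminar level.

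**What to change.** For each primary outcome, replace the ANOVA with a mixed model that includes seminar random effects and takes one of two forms:

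- (a) T0, T1 and T2 as outcomes, with the T0 mean constrained equal between arms; or
- (b) T1 and T2 as outcomes, with the individual T0 score and the seminar-mean T0 as covariates, each by time.

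Test the group effect at T1 and T2 jointly (2 df). Report the adjusted difference with a 95% confidence interval at T1 and at T2 whether or not the joint test is significant. Use the same structure for the profession model.

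The cost is a change of wording in section 6.4.2, made before outcome data are analysed. No new data are needed, and the mixed-model procedure in SPSS, the named software, can fit it. There is one small downside: with few seminars, the seminar-mean covariate in (b) uses up seminar-level degrees of freedom.

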6.3.1. Primary outcomes

- **Stereotype endorsement**^{9,12}: Agreement to negative stereotypes about people with psoriasis will be assessed using a scale consisting of 11 adjective pairs (e.g., unattractive – attractive). Participants were asked to mark the circle closest to the adjective they

considered to describe a person with psoriasis (range: 1–5). Scores will be averaged, with higher scores reflecting stronger endorsement of negative stereotypes.

- **Disease-related misconceptions^{9,12}:** To measure agreement with common misconceptions about psoriasis, participants will indicate their degree of agreement with 15 statements (e.g., “Psoriasis is contagious.”) on a 5-point Likert scale ranging from “strongly disagree” to “strongly agree”. Scores will be averaged, higher scores reflecting stronger endorsement of these misconceptions.
- **Desire for social distance^{9,12}:** Participants will rate their desire for social distance towards persons with psoriasis in nine situations (e.g., shaking hands) on a 5-point Likert scale ranging from “definitely not” to “definitely”. Scores will be averaged, higher scores reflecting a higher desire for distance.
- **Reported and intended behaviour¹³:** The Reported and Intended Behavior Scale consists of four items assessing the presence of behaviour (yes/no) in each of four contexts (living together with, working with, living nearby, and continuing a relationship with someone affected by a chronic skin disease) and four more items assessing intended behaviour in these contexts in the future, rated on a 5-point Likert scale ranging from “strongly disagree” to “strongly agree”. A sum score across the four “future behaviour” items will be calculated, with lower scores indicating more stigmatising behaviour.

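### The Bonferroni family for the four primary outcomes is not named; naming it fixes the error rate, and Holm over the four Group x Time tests never does worse than Bonferroni over the same four

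*Protocol*

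**What the plan says.** Section 6.3.1 gives four primary outcomes: stereotype endorsement, disease-related misconceptions, desire for social distance, and reported and intended behaviour. None is ranked above the others. Section 5.1 hypothesises a larger reduction in stigmatising attitudes without saying which of the four, or how many, must show it.

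Section 6.4.2 plans three layers of tests on these outcomes:

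- a Group x Time repeated-measures ANOVA for each primary outcome;
- a Group x Time x Profession ANOVA for each;
- pairwise comparisons to follow up significant effects.

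On the error rate it says "The significance level will be established at a p-value ≤ 0.05" and then "Bonferroni correction for multiple testing will be applied". It gives neither the family nor the divisor.

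Section 6.2.1 sizes the trial for one test ("F-tests for repeated measures ANOVA, within-between interaction") at an uncorrected 0.05, using the effect for behavioural intentions only. This gives 82 participants. The target is then raised to 120 to cover multiplicity and up to 20% dropout together, with no corrected level stated.

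**The concern.** The section fixes a level and a method but not the number that turns them into a decision rule. At least three readings fit the wording:

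- only the pairwise comparisons are corrected, so each primary test runs at 0.05;
- the four primary tests are corrected, so each runs at 0.0125;
- the four two-way and four three-way ANOVAs are corrected together, so each runs at 0.05/8 = 0.00625, and lower still if pairwise tests are counted.

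A primary p-value of 0.03 is positive on the first reading and negative on the second. A p-value of 0.01 is positive on the second and negative on the third. If the reading is settled only after the data are seen, the multiplicity control loses its purpose.

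There is also a question of efficiency. On the sensible reading the planned method is valid, but a better one is available for the same family and needs no further assumption.

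**Working it through.** **Inputs.** From the protocol: four primary outcomes (6.3.1); 2 groups and 3 time points (6.4.2); partial eta squared 0.02, level 0.05, power 0.80, 82 participants, 120 enrolled and up to 20% dropout (6.2.1). Completers: 120 x 0.8 = 96. Assumed, because the protocol does not state them: within-person correlation 0.5, sphericity, equal groups, independent participants, and inter-outcome correlation 0.3-0.7.

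**Reproducing the 82.** f² = 0.02/0.98 = 0.0204. For the within-between interaction, λ = f² x N x 3/(1 − 0.5) = f² x 6N, with df1 = 2 and df2 = 2(N − 2). At N = 82, λ = 10.04 and power at 0.05 is 0.809. The formula needs 81, or 82 with equal groups, so the protocol's figure is reproduced.

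**Familywise error over the four primary tests.**

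- Each at 0.05, independent outcomes: 1 − 0.95⁴ = 0.185.
- Each at 0.05, simulated at inter-outcome correlation 0.3 / 0.5 / 0.7: 0.176 / 0.158 / 0.132.
- Each at 0.0125, independent outcomes: 1 − 0.9875⁴ = 0.049.

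**Power per outcome under each reading, 96 completers.** λ = 0.0204 x 576 = 11.76 and df2 = 188.

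| Level per primary test | Power |
|---|---|
| 0.05 (primary tests uncorrected) | 0.871 |
| 0.0125 (four primary tests) | 0.722 |
| 0.00625 (four plus four profession ANOVAs) | 0.64 |

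At 0.0125 the same formula needs 112 completers for 80% power, that is 112/0.8 = 140 enrolled.

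**Holm against Bonferroni/4.** Holm compares the ordered p-values with 0.05/4, 0.05/3, 0.05/2 and 0.05, and stops at the first failure. The first step is the Bonferroni threshold and the later ones are more lenient. Holm therefore rejects everything that Bonferroni rejects, and the chance of at least one rejection is identical. Simulated power per truly affected outcome, with 96 completers and Bonferroni/4 at 0.722:

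| Outcomes with the planning effect | Gain from Holm |
|---|---|
| Four | about 7-9 points (Holm 0.815 / 0.807 / 0.801 at correlation 0.3 / 0.5 / 0.7) |
| Three | about 4-5 points |
| Two | about 2 points |
| One | about 0.1 point |

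The range for four outcomes covers both the F-test simulation and a 2-df chi-square approximation (Bonferroni 0.735, Holm 0.809-0.826). Holm's simulated familywise error was at most about 0.05 in every scenario.

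**The case against.** The strongest reply is that 0.05 followed at once by Bonferroni reads naturally as an overall level that is then divided. A reader might infer that the two sentences contradict each other. They do not: the fault is an unnamed family, and a SAP, which was not available here, may name it.

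The text also leans against the damaging reading. Section 6.2.1 cites multiplicity as a reason for the larger sample, which suggests that the main tests are to be corrected. In section 6.4.2 the Bonferroni sentence follows the ANOVA and significance-level sentences, and the pairwise comparisons come later. The 18.5% is therefore the consequence of one possible reading, not of the plan as most would read it.

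A reader might also infer that Holm is what controls the error rate, or that it returns 7-9 points of power whatever happens and at no cost. Neither is supported. Bonferroni over the four named tests controls the error equally well. The 7-9 points require all four outcomes to carry an effect that section 6.2.1 gives for one of them only. The results reported in section 5 for the earlier intervention, which improved social distance, stereotypes and false assumptions, make a broad effect plausible but do not give its size on each outcome.

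What survives is narrower. The family is not stated, and over the sensible family Holm rejects everything that Bonferroni rejects, and sometimes more.

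**Conclusion.** The point holds as a cheap improvement, not as an error that invalidates the plan. Naming the four Group x Time tests as the family controls the familywise error. Replacing Bonferroni/4 by Holm then adds between almost nothing and about 9 points of power per outcome, depending on how many outcomes respond.

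The power figures are conditional:

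- With a within-person correlation of 0.7 instead of 0.5, Bonferroni power at 96 completers is already 0.94 and the gain is about 3 points (all four effects real, inter-outcome correlation 0.5).
- If the cited partial eta squared is on the scale that SPSS reports, λ = f² x (N − 2) x 2. Bonferroni/4 power is then about 0.21, and the gain about 3 to 4 points with all four effects real.
- Section 6.1 allocates seminars, not persons, so true power is probably lower than all figures here.

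That Holm rejects at least as much as Bonferroni over the same four tests depends on none of these assumptions. Against testing each outcome at an uncorrected 0.05, Holm has lower power: 0.871 falls to about 0.79-0.83 with all four effects real (inter-outcome correlation 0.9 to 0) and to 0.72 with one. That is the price of error control.

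**What to change.** Replace the Bonferroni sentence in section 6.4.2, before the data are analysed, by:

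> The four Group x Time interaction tests, one per primary outcome, form one family and are tested with the Holm procedure at a familywise level of 0.05. Post-hoc pairwise comparisons are made only after a significant interaction and are Bonferroni-corrected within each outcome; profession interactions and secondary outcomes are exploratory.

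The text should name the interaction: in a repeated-measures ANOVA a between-group test can be taken for the Group main effect. It should not call the level two-sided, which has no meaning for a 2-df F-test.

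The change needs no further data or participants. Its costs are that Holm has no simple matching simultaneous confidence intervals, and that the profession analyses lose any confirmatory standing, which the sponsor should accept explicitly. If matching intervals matter more than the extra power, Bonferroni over the same four named tests is an acceptable alternative; the essential part is naming the family.
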